Primary Endpoint:	The primary endpoint of this study is the incidence of complete wound closure, as assessed by the Investigator at or before Week 12 of the Treatment Phase, which is confirmed closed two weeks later. Complete wound closure is defined as complete skin re-epithelialization that is without drainage or dressing requirements
Secondary Endpoint(s):	1. The proportion of subjects in each group with complete closure of the study ulcer at or before Week 12 as assessed by computerized planimetry.

	
 2. The proportion of subjects in each group with complete wound closure of the study ulcer at or before Week 12 as assessed by independent, blinded, assessment of photographs. 3. The time to complete wound closure, as assessed by the Investigator. 4. The time to complete wound closure for all closed wounds in each group, as assessed by computerized planimetry. 5. For those wounds that have closed, the rate of wound closure for each group, as assessed by computerized planimetry. 6. Medical resource utilization associated with management of DFU and related complications as determined by a comparison of estimated costs from the presumed billing codes which would have been used for each patient.

Safety Endpoint:
	
Incidence of all investigational product, procedure, and/or wound-related adverse events or serious adverse events.

Exploratory Endpoint(s):
	
 1. The proportion of closed wounds in each group at Week 4 of the Treatment Phase 2. Co-variate analyses of the primary endpoint using those listed in section 9.3.

Description of Study Intervention(s):
	
Intervention 1: SOC therapy consisting of the use of moist wound dressings, debridement, infection surveillance and management and consistent and appropriate use of an offloading boot.
 
Intervention 2: AMNIOEXCEL Plus used in conjunction with SOC therapy.
 
Intervention 3: Apligraf used in conjunction with SOC therapy.

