
Subject Duration:
	
All subjects will have a SOC screening period of up to 2 weeks ± 3 days prior to randomization (Day 0). Investigational product with SOC treatments or SOC alone treatments will begin on Day 0 (randomization) and will be applied weekly for up to 11 weeks ± 3 days. If the wound closes on or before week 11, follow-up will begin and will last 2 weeks ± 3 days after the date of closure. If the wound does not close by week 12, the subject will be immediately exited from the study and no further follow-up will occur as part of the study. The total duration for a single subject may last up to 16 weeks ± 3 days.

Statistical Methods & Analyses:
	
This is a prospective, multicenter, parallel-group, randomized, three-arm trial designed to assess the proportion of subjects achieving complete wound closure of their DFUs, in a population with adequate arterial circulation, following up to 11 weeks of treatment receiving either AMNIOEXCEL Plus Placental Allograft Membrane with SOC, Apligraf bi-layered skin substitute with SOC, or SOC alone. Subjects will be randomized 1:1:1, to receive either

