8.3. Safety Population

The Safety population is defined as all subjects receiving the allocated treatment after randomization. This population will be used for the analysis of safety endpoints.

9. Description of Efficacy Endpoints and Analyses

The primary analysis of the primary efficacy endpoint will be performed using the ITT population. The sensitivity analysis of the primary endpoint will be performed using the PP population. All secondary efficacy endpoints will be performed using the ITT population. Safety analysis will be based on the safety population.

In efficacy or exploratory analyses, covariate analyses will be conducted to assess the impact of various prognostic factors on closure and to demonstrate the robustness of the primary analysis. Prognostic factors (i.e., covariates) will be included if they are found to be contributing factors (i.e., the individual covariate p-value is less than 0.10). Potential prognostic factors to be considered include:

• Ulcer area

Duration of ulcer

Gender

• HbA1c

•Ulcer Location

Diabetes type

• Race

• Nicotine Use

Baseline BMI

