9.5. Missing Data

For primary efficacy evaluation of data points, the last available observation (LOCF) will be used. In the analyses of using the planimetry data, the last available planimetric value will be used for a discontinued subject. All subjects discontinued during the treatment period and before 100% wound closure during the treatment phase of the study will not be replaced and will be considered treatment failures for evaluating the primary and secondary endpoints.

10. Description of Other Variables and Analyses

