11.1.2. Standard calculations

The following calculations will be used:

Equation 1. Age of Ulcer

$$Age = int \left(\frac{(date\ of\ ulcer\ at\ baseline - date\ of\ birth + 1)}{365.25} \right)$$

Equation 2. Clinical Trial Duration for a Subject

For subjects completing the study:

2a) Duration (days) = Final Follow up visit date - Randomization Visit Date

If a subject has not finished treatment (e.g., withdrawals, loss-to-follow-up, etc.)

2b) $Duration_{Withdrawal}(days) = Date \ of \ Withdrawal - Randomization \ Date + 1$

Equation 3. Duration of Adverse Events

 $Duration_{AE} = Onset\ Date_{AE} - Randomization\ Date_{AE} + 1$

Equation 4. Time to Complete Wound Closure

4a) Days to Complete Wound Closure $_{Investigator-based} = (Date\ of\ Last\ Confirmation\ Visit_{EDC}) - (Randomization\ Date) + 1$

Important: This metric will only be calculated for subjects who achieve investigator-based complete wound closure.

EDC: Indicates closure as defined in the EDC system; the investigator-noted closure.

Confidential Page 20 of 23

4b) Days to Complete Wound Closure_{Planimetric} = (Date of Last of Two Successive Readings of $0cm^2_{TA}$) – (Randomization Date) + 1

Important. Planimetric wound closure will only be calculated for subjects who achieve planimetric-based complete wound closure during the Treatment Phase.

TA: Size from imaging vendor (Tissue Analytics, Inc.) database.

Equation 5. Rate of Wound Closure

Rate of Wound Closure (
$$^{\%}$$
 Area/ $_{Week}$) = $\frac{7 \times (Area_{baseline} - Area_{final})}{Area_{baseline} \times Duration}$

Equation 6. Costs Associated with Applied CPT or DRG Codes

- 6a) $CPT\ Total\ Cost_{Study-Wide} = \sum Estimated\ Cost_{All\ Cohorts}$
- 6b) $CPT\ Total\ Cost_{Cohort\ X} = \sum Estimated\ Cost_{Schort\ X}$
- 6c) CPT Average $Cost_{Study-Wide} = \frac{\sum Estimated Costs_{Study-Wide}}{n_{all costs}}$
- 6d) $CPT \ Average \ Cost_{Cohort \ X} = \frac{\sum Estimated \ Costs_{Cohort \ X}}{n_{cohort-based \ costs}}$

Estimated Costs are based on CPT-10 codes.

Equation 7. Costs Associated with Use of Product

- 7a) $Cost \ All \ Product_{Study-Wide} = \sum Costs \ Per \ Product_{All \ Cohorts}$
- 7b) $Cost \ All \ Product_{Cohort \ X} = \sum Costs \ Per \ Product_{Cohort \ X}$

Confidential Page 21 of 23

7c) Average Cost All Product_{Study-Wide} =
$$\frac{\sum Costs \ Per \ Product_{Study-Wide}}{n_{all \ costs}}$$

7d) Average Cost All Product_{Cohort X} =

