11.1.3. Other Variables

Discontinuations

The difference between treatments, both overall and for each primary reason, will be compared by using a 2-sided Fisher's exact test.

Confidential Page 22 of 23

Demographic and Baseline Characteristics

Comparisons between treatment groups of continuous variables will be made by using a one-way analysis of variance with treatment as a factor. For categorical variables, the Fisher's exact test will be used. All tests will be 2-sided and performed at the 0.05 level of significance.

Time-to-Event Data

Time-to-event endpoints including time-to-complete-wound-closure/healed will be evaluated using the Kaplan-Meier method. The log-rank test will be used to compare the distributions between two treatment groups.

Rate of Wound Closure, as Assessed by Computerized planimetry

Analysis of Covariance (ANCOVA) will be used to compare the rate of wound closure for the two treatment groups.

Safety Data

The primary safety endpoint for this study is any severe device-related complication where relationship to the device was assessed by the clinical event committee possible, probably, or definite. Fisher's exact test will be used to compare incidence rates of serious device-related complications as well as for any device-related complication, and for specific complications between the treatment group and the control group.

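### SAP Equation 4 defines time to closure only for wounds that close, and no censoring rule covers the rest, which contradicts the SAP's own ITT and failure rules

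*SAP*

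**What the plan says.** Time to closure is a secondary endpoint in two versions, investigator-assessed and planimetric. SAP 11.1.2 contains the only derivation rules. For Equation 4a: "This metric will only be calculated for subjects who achieve investigator-based complete wound closure". For Equation 4b: "Planimetric wound closure will only be calculated for subjects who achieve planimetric-based complete wound closure during the Treatment Phase". Both notes are flagged as important. The protocol synopsis words the planimetric version as "The time to complete wound closure for all closed wounds in each group, as assessed by computerized planimetry".

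SAP 11.1.3 then sets the analysis: "Time-to-event endpoints including time-to-complete-wound-closure/healed will be evaluated using the Kaplan-Meier method" and "The log-rank test will be used to compare the distributions between two treatment groups". SAP 9.2 also allows a Cox model.

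Three other statements bear on subjects who do not close:

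- SAP 9, opening text: "All secondary efficacy endpoints will be performed using the ITT population".
- SAP 9.5, on subjects discontinued before closure: they "will not be replaced and will be considered treatment failures for evaluating the primary and secondary endpoints".
- Protocol synopsis, Subject Duration: "If the wound does not close by week 12, the subject will be immediately exited from the study".

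Neither document states a censoring rule, a censoring date or a time value for a subject whose wound does not close.

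**The concern.** A programmer who follows Equation 4 as written has a missing time for every wound that does not close, and survival software drops records with a missing time. The Kaplan-Meier curve then contains no open wounds. It reaches 100% closed in every arm, and its median is the median among healers.

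That compares groups selected by the outcome. A product that also closes slow wounds adds late closers and looks slower; one that closes only easy wounds looks fast. The secondary objective asks about each randomized arm, and a closers-only analysis does not answer it. It also cannot be reconciled with the ITT statement in SAP 9 or the failure rule in SAP 9.5.

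**Working it through.** **1. The plan's own figure.** The only design figure is the 13.5% half-width (Protocol 9.2, SAP 5), from 38 per arm and 90% closure. It reproduces as the half-width for a difference between two arms: 1.96 × √(2 × 0.90 × 0.10 / 38) = 13.49%. A single rate gives 1.96 × √(0.90 × 0.10 / 38) = 9.5%. It does not bear on time to closure. The documents give no hazard ratio, event count or closure timing, so every closure rate and timing below is an assumption.

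**2. Who has a time under Equation 4a.**

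- Closed and confirmed: yes, dated at the last confirmation visit.
- Open at Week 12: none.
- Closed but open again at follow-up (a failure under SAP 9.1): none.
- Discontinued before closure (a failure under SAP 9.5): none.

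**3. What this does to the curve.** Let F(t) be the proportion of an arm closed by week t, and p = F(12). With all subjects, the curve ends at p. With closers only, it is F(t)/p and ends at 100%, so any difference in p cancels. At 70% against 40% with 38 per arm, the expected closers are 26.6 and 15.2. The analysis drops 11.4 + 22.8 = 34.2 of 76 subjects, or 45%.

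**4. Simulation.** Two-sided 0.05 log-rank test, weekly visits to Week 12, 38 per arm, 2,000 runs per scenario. The all-subjects analysis censors non-closers at Week 12. Under proportional hazards with hazard ratio 2, treatment closure is 1 − (1 − control)².

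| Assumed scenario | All subjects: detects better arm | Closers only: detects better arm | Closers only: significant for worse arm |
|---|---|---|---|
| 70% vs 40%, closure uniform on Weeks 2–12 in both arms | 72% | 2–3% | 3.4% |
| 75% vs 40%, same timing | 87% | 3% | 3% |
| Hazard ratio 2: 51% vs 30% | 48% | 5% | 2% |
| Hazard ratio 2: 64% vs 40% | 57% | 5% | 1% |
| Hazard ratio 2: 75% vs 50% | 65% | 9% | 0.4% |
| Hazard ratio 2: 84% vs 60% | 73% | 14% | 0.2% |
| Proportional hazards: 90% vs 70% | 71% | 20% | 0.1% |
| 35% early + 35% late vs 35% early + 5% late (Weeks 2–7, 8–12) | 55–57% | 0% | 60–61% |
| 40% in Weeks 2–8 + 35% in Weeks 8–12 vs 40% in Weeks 2–8 | 67% | 0% | 90% |

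The eighth row shows how reversal arises. Among closers, the late share is 35/70 = 50% in the better arm and 5/40 = 12.5% in the worse one, with closers-only medians of 7.4 and 4.9 weeks.

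With no true difference, the two-sided error is 4.7% (all subjects) and 4.8% (closers only) at 90% closure, and 4.4% and 5.8% at 50%. With 30 per arm after 20% attrition (38 × 0.8 = 30.4), the pattern holds: hazard ratio 2 gives 41–62% against 4–13%.

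**5. Dates matter for the remedy.** Equation 4a dates a closure at its last confirmation visit, about two weeks after it was noted. Non-closers exit at Week 12. If non-closers are added and censored at Week 12 while that event date is kept, closures at Weeks 11–12 become events at Weeks 13–14, after every failure has left the risk set. Simulated this way, detection is 54% instead of 72% in the first scenario and 23% instead of 55–57% in the eighth. The better arm's curve still reaches 100% in over 99% of runs. If non-closers are instead held at risk to Week 14, all event times shift by the same two weeks, their order is unchanged, and so is the log-rank statistic.

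**The case against.** A reader might infer that the plan states that failures are left out of the log-rank test. It does not. Equation 4 sits among the standard calculations and defines a number of days that does not exist for an open wound. The choice of Kaplan-Meier, the ITT statement and the failure rule all suggest that non-closers were meant to be kept and censored. The closed-wounds wording is in one synopsis line, for planimetry only. Protocol Table 3, Protocol 9.1 and SAP 9.2 state both time endpoints without it, and SAP 9.2 applies such a restriction only to the closure rate.

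That argument stands as to intent, and it limits the claim to what follows if Equation 4 is applied as written. It does not remove the defect. Censoring has to be inferred against an explicit restriction, and even then no censoring time is given. SAP 9.4 extends the closure rate to all and to non-healed wounds but makes no such extension for time to closure.

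A reader might also infer that a closers-only test generally reverses a real effect. Reversal appears only where the extra closures come late. Under proportional hazards the direction is kept on average, and significant results the wrong way are about 2% or fewer.

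On weight, Protocol 9.4.6 calls the secondary analyses exploratory and SAP 5 says the study is not adequately powered for hypothesis testing. Both points stand.

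**Conclusion.** The point holds as an internal contradiction. Both time variables exist only for closers, no censoring rule is given, and SAP 9 and SAP 9.5 require the other subjects to count. Applied literally, the analysis loses most of its ability to show a real difference: 72% falls to about 2–3% when treatment changes how many wounds close but not when, and 48–73% falls to 5–14% at hazard ratio 2 with 30–60% control closure. It can point the wrong way only if the extra closures are late.

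These sizes rest on assumed closure rates and timing. At the plan's own assumption of 90% closure and no difference, about 4 of 38 per arm would drop out (0.10 × 38 = 3.8) and false positives would not increase. The primary endpoint is unaffected. The point should be corrected before the time-to-closure results are interpreted, but it does not threaten the trial's main result.

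**What to change.** 1. Delete the two restrictions to closers under Equations 4a and 4b. Drop the closed-wounds qualifier from the planimetric time endpoint in the synopsis, or record the departure in SAP 12.
2. Give every ITT subject a time record. Confirmed closure is the event. All others, including wounds that reopen and SAP 9.5 failures, stay at risk and are censored at a common horizon no earlier than the last possible event time. State how the undetermined closures of SAP 9.1 are coded.
3. Put events and censoring on one time scale. Either date a confirmed closure at the visit where it was first noted and censor at Week 12, or keep the confirmation date and hold non-closers at risk to Week 14. If actual days are used, the horizon must cover the visit window: Week 12 is day 84 ± 3, so a closure can be dated up to 84 + 3 + 1 = 88 on Equation 4's count. Apply the same principle to Equation 4b, whose event date is the second of two successive zero readings.
4. Run Kaplan-Meier, log-rank and any Cox model on this set. Report days to closure among closers as a descriptive line only.

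The cost is SAP wording and one derived variable from data the study already collects. Medians may be later than the closers-only figures or may not be reached.

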1 PROTOCOL SUMMARY

Table 1: Protocol Synopsis

Title:	A Prospective, Multi-Center, Randomized, Parallel-group Study Comparing AMNIOEXCEL Plus Placental Allograft Membrane to Apligraf Bi-layered Skin Substitute and Standard of Care Procedures in the Management of Diabetic Foot Ulcers
Short Title:	AMNIOEXCEL Plus vs Apligraf vs Standard of Care (SOC) in the Management of Diabetic Foot Ulcers
Study Description:	This is a multicenter, randomized, parallel-group study comparing the outcomes associated with the use of AMNIOEXCEL Plus Placental Allograft Membrane, Apligraf bi-layered skin substitute and SOC alone in the management of diabetic foot ulcers (DFUs).
Pre/Post-Market:	Post-Market
Study Design:	This study will have three (3) phases: (1) a Screening Phase, (2) a Treatment Phase, and (3) a Follow-up Phase. Subjects will be seen weekly in the Screening and Treatment Phases. Subjects who achieve wound closure during the Treatment Phase will be entered into the Follow-up Phase and will return to the site for up two (2) additional weeks for confirmation visits. An interim analysis will occur after 50% of subjects have reached the primary endpoint.
Primary Objective:	The primary objective of this study is to compare outcomes associated with the use of AMNIOEXCEL Plus Placental Allograft Membrane, Apligraf living, bi-layered skin substitute and SOC in the management of DFUs.
Secondary Objective(s):	The secondary objectives of this study are to: 
 1. Determine the proportion of subjects in each study arm with complete closure of the study ulcer at or before 12 weeks of treatment 2. Determine the time to complete wound closure in each study arm 3. Determine the rate of wound closure in each study arm 4. Assess medical resource utilization outcomes in each study arm
Safety Objective:	The safety objective of this study is to assess adverse events associated with any of the investigational products and/or study procedures in the management of DFUs.
Exploratory Objective(s):	The exploratory objectives of this study are to: 
 1. Determine the proportion of subjects in each cohort whose wounds are closed at 4 weeks of treatment. 2. Determine the effect of any covariate on the primary endpoint.

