3 OBJECTIVES AND ENDPOINTS

Table 3: Objectives and Endpoints

OBJECTIVES	ENDPOINTS
Primary	
The primary objective of this study is to compare outcomes associated with the use of AMNIOEXCEL Plus Placental Allograft Membrane, Apligraf living, bi-layered skin substitute and SOC in the management of DFUs.	The primary endpoint of this study is the incidence of complete wound closure, as assessed by the Investigator at or before Week 12 of the Treatment Phase and confirmed 2 weeks later. Confirmed complete wound closure is defined as complete skin re-epithelialization that is without drainage or dressing requirements.
Secondary	
1. Determine the proportion of subjects in each study arm with complete closure of the study ulcer at or before 12 weeks of treatment	1. Proportion of subjects with complete closure of the study ulcer at or before Week 12 and confirmed 2 weeks later as assessed by computerized planimetry. 2. Proportion of subjects with complete wound closure of the study ulcer at or before Week 12 and confirmed 2 weeks later as assessed by independent, blinded, assessment of photographs.
2. Determine the time to complete wound closure in each study arm	1. Time to complete wound closure, as assessed by the Investigator. 2. Time to complete wound closure, as assessed by computerized planimetry.
3. Determine the rate of wound closure in each study arm	1. Rate of wound closure, as assessed by computerized planimetry.
4. Assess medical resource utilization outcomes in each study arm	1. Medical resource utilization associated with treatment of DFU and related complications as determined by a comparison of estimated costs from the presumed billing codes which would have been used for each patient.
Exploratory	
1. The proportion of subjects in each cohort whose wounds are closed at 4 weeks of treatment.	1. Wound closure status at Week 4 of Treatment
2. The effect of any covariate on the primary endpoint.	1. Co-variate analyses of the primary endpoint using those listed in section 9.3.
Safety Endpoints	
The safety objective of this study is to assess adverse events associated with either of the study treatments and/or all study procedures in the management of DFUs.	Incidence of all treatment, procedure, and/or wound-related adverse events or serious adverse events in any of the study cohorts.

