9.1 STATISTICAL ENDPOINTS

- Primary Efficacy Endpoint(s):

The primary endpoint of this study is the incidence of complete wound closure, as assessed by the Investigator at or before Week 12 of the Treatment Phase and confirmed closed 2 weeks later. Confirmed complete wound closure is defined as complete skin re-epithelialization that is without drainage or dressing requirements two weeks later.

A subject is considered to have a closed wound (i.e., a closure success) if the subject's treated wound closes between week 1 and 12 and is noted as closed on both follow-up visits.

A subject is considered to not have a closed wound (i.e., a closure failure) if they meet any of the following:

- the subject's treated wound does not close by week 12
- the subject's treated wound closes between week 1 and 12 and is noted as open on either or both of the follow-up visits.

A subject is considered to have an undetermined wound closure if the subject's treated wound closes between week 1 and 12 and the subject misses either or both of the follow-up visits. These subjects may become part of extended analyses.

- Secondary Efficacy Endpoint(s):
 1. Proportion of subjects with complete closure of the study ulcer at or before Week 12 as assessed by computerized planimetry.
 2. Proportion of subjects with complete wound closure of the study ulcer at or before Week 12 as assessed by independent, blinded, assessment of photographs.
 3. Time to complete wound closure, as assessed by the Investigator.
 4. Time to complete wound closure, as assessed by computerized planimetry.
 5. Rate of wound closure, as assessed by computerized planimetry.
 6. Medical resource utilization associated with treatment of DFU and related complications as determined by a comparison of estimated costs from the presumed billing codes which would have been used for each patient.

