9.2. Secondary Endpoint Analysis

The secondary endpoints that will be analyzed as part of this trial are as follows:

• Proportion of subjects with complete closure of the study ulcer at or before Week 12 and confirmed 2 weeks later as assessed by computerized planimetry.

Confidential Page 14 of 23

- Proportion of subjects with complete wound closure of the study ulcer at or before Week 12 and confirmed 2 weeks later as assessed by independent, blinded, assessment of photographs.
- The Time to complete wound closure, as assessed by the Investigator.
- The Time to complete wound closure, as assessed by computerized planimetry.
- For those wounds that have closed, the rate of wound closure for each group, as assessed by computerized planimetry.
- Medical resource utilization associated with management of DFU and related complications as determined by a comparison of estimated costs from the presumed billing codes which would have been used for each patient. The summary will be provided by an independent group, results will not be included in this analysis

Proportion of ulcers with complete wound closure during the treatment phase as assessed by planimetry will be compared using Logistic Regression with specified baseline covariates in the model.

Time to complete wound closure will be analyzed using the Log-rank test or Cox Proportional Regression Model. The Kaplan-Meier methods will be used to present the distribution of time to complete wound closure.

Summary statistics will be provided for the rate of wound closure for the two treatment groups.

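### Planimetric closure is stated both with and without confirmation and timed by a third rule, and Equation 4b dates it one visit late

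*SAP*

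**What the plan says.** Three versions of planimetric closure stand in the current text.

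- **Unconfirmed.** The Protocol synopsis gives secondary endpoint 1 as "The proportion of subjects in each group with complete closure of the study ulcer at or before Week 12 as assessed by computerized planimetry". Protocol 9.1 repeats it without the group wording. The analysis sentence in SAP 9.2, matched in Protocol 9.4.6, also has no confirmation: "Proportion of ulcers with complete wound closure during the treatment phase as assessed by planimetry will be compared using Logistic Regression".
- **Confirmed.** Protocol Table 3 words the same endpoint as closure "at or before Week 12 and confirmed 2 weeks later as assessed by computerized planimetry", and the endpoint list that opens SAP 9.2 follows it.
- **Two zeros.** SAP 11.1.2, Equation 4b, computes planimetric time to closure from the "Date of Last of Two Successive Readings of" 0 cm², minus the randomization date, plus 1. A note under it adds: "Planimetric wound closure will only be calculated for subjects who achieve planimetric-based complete wound closure during the Treatment Phase".

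The investigator-based counterpart, Equation 4a, runs from randomization to the last confirmation visit and is likewise computed only for subjects who close. On the visit schedule, the synopsis says: "Subjects who achieve wound closure during the Treatment Phase will be entered into the Follow-up Phase". SAP section 12 records changes for the photograph review and the Week 4 status only.

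**The concern.** The SAP cannot settle the matter by taking precedence over the Protocol, because SAP 9.2 lists the confirmed endpoint and then describes an analysis of closure with no confirmation. Equation 4b supplies the only operational rule, and it matches neither version. The closure proportion, the logistic model and the time analysis could therefore each count a different set of wounds as closed. The choice also feeds the rate of closure (SAP 9.2 restricts it to closed wounds) and the healed/non-healed splits in SAP 9.4.

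Planimetry carries some weight here. The trial is open label with no analytical blinding (Protocol 6.3), the primary endpoint is the investigator's judgement, and SAP section 12 drops the blinded photograph review. Planimetry is then the only remaining closure measure that does not rest on that judgement.

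A separate problem lies in the dating. Equations 4a and 4b both date closure at a confirming visit, and not at the same one.

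**Working it through.** The plan gives no figure on this point, so there is none to reproduce.

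**Inputs.** Weekly visits, each ±3 days (Protocol Table 2, 8.1.4). Two weekly follow-up visits after closure, the second only if the wound is still closed at the first (Table 2, footnote b). Images scheduled at all these visits, except that Week 1 is not required in the Apligraf arm (8.1.4). 38 subjects per arm (Protocol 9.2). Equations 4a and 4b (SAP 11.1.2).

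**Step 1: classification.** Take the reading at the first zero and at the next two visits. Confirmation is taken to mean closed at both follow-up visits, as for the primary endpoint in SAP 9.1.

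| Readings | Unconfirmed | Two zeros, Follow-up images count | Confirmed |
|---|---|---|---|
| 0, open | closed | not closed | not closed |
| 0, 0, open | closed | closed | not closed |
| 0, 0, 0 | closed | closed | closed |

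**Step 2: the phase clause in Equation 4b.** If only the first zero must fall in the Treatment Phase, the third column applies as shown. If both zeros must, a wound first at zero at Week 12 fails, because its next image is at Week 13. So does a wound at any week where the investigator calls closure at the first zero visit, because the next image is then a Follow-up image. The text does not say which reading is meant.

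**Step 3: size.** One reclassified subject is 1/38 = 2.6 percentage points of an arm. The documents give no re-opening rate, so the following is an illustration on an assumption: of 30 wounds reaching a first zero, each later weekly reading is independently non-zero with probability q.

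| q | Unconfirmed: 30 | Two zeros: 30(1−q) | Confirmed: 30(1−q)² |
|---|---|---|---|
| 5% | 30 | 28.5 | 27.1 |
| 10% | 30 | 27.0 | 24.3 |
| 20% | 30 | 24.0 | 19.2 |

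At q = 10%, the unconfirmed and confirmed counts differ by 30 − 24.3 = 5.7 wounds, or 5.7/38 = 15.0 points of an arm. This is a change in level; it does not show a difference between arms.

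**Step 4: dates.** Equation 4b lags the first zero by 7 days nominally. With both visits inside their windows the range is 7 ± 6 = 1 to 13 days, and more if an image is missed. Equation 4a lags first closure by 14 days nominally, with range 14 ± 6 = 8 to 20. If both assessments first show closure at the same visit, the study days are:

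- Week 8: first zero 56 + 1 = 57; Equation 4b 63 + 1 = 64; Equation 4a 70 + 1 = 71.
- Week 12: first zero 84 + 1 = 85; Equation 4b 91 + 1 = 92; Equation 4a 98 + 1 = 99.

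**Step 5: arm symmetry.** The one-visit lag is nearly the same in every arm. The exception is the Apligraf Week 1 image. Without it, the earliest nominal Equation 4b date is day 22 (zeros at Weeks 2 and 3), against day 15 (Weeks 1 and 2) in the other arms.

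**The case against.** Equation 4b can be defended as a timing formula that takes closure status as given. On that view the Treatment Phase wording applies to achieving closure and not to the second reading. This parallels the primary endpoint, where closure comes by Week 12 and confirmation follows. It is a natural reading, and under it Week 12 closures count. A reader might infer that wounds first closed at Week 12 can never qualify, but that holds only if both zeros must fall in the Treatment Phase, which the SAP does not say. What remains is that the clause is open to both readings, and that the status Equation 4b presupposes is not settled elsewhere.

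The SAP 9.2 analysis sentence may simply name the model for the endpoint listed above it, with the phase wording standing in for the Week 12 limit. That is possible, but the synopsis and Protocol 9.1 are endpoint statements in their own right and omit confirmation.

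Dating closure at confirmation is a convention, and a delay common to all arms barely affects a log-rank test. This stands. It is also fair that the planimetry analyses are labelled exploratory (Protocol 9.4.6), that the study is not powered for hypothesis testing (SAP section 5), and that the primary proportion is unaffected.

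**Conclusion.** The point holds as a definitional gap in a secondary endpoint, together with a separate dating problem. It should be fixed, but it does not threaten the primary result.

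- **Definition.** A wound at zero and then open at the next visit is closed under the unconfirmed version only. A wound at zero twice and then open is closed under the unconfirmed version, and under Equation 4b if Follow-up images count, but not under the confirmed version. Each such subject moves an arm by 2.6 points. How many there will be cannot be known from the documents.
- **Dating.** Equation 4b is one visit late (nominally 7 days, 1 to 13 within windows) and Equation 4a two visits late (nominally 14 days). Reported medians are inflated and the two time endpoints cannot be compared directly. The effect on between-arm log-rank comparisons is small.

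Two stronger inferences are not supported. A reader might take the late dates to be a result of the competing definitions; they come from the equations themselves and would remain if one definition were chosen. A reader might also infer a fixed 7-day gap between investigator and planimetric times. That requires both assessments to show closure at the same visit, which no section states, and the visit windows widen it in any case.

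**What to change.** Use one definition in Protocol 9.1, SAP 9.2 (endpoint list and logistic model) and Equation 4b, and carry it to the synopsis and Protocol 9.4.6: first 0 cm² image at or before Week 12, confirmed by 0 cm² at both follow-up images. State that Follow-up images count for confirmation. Then:

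- Date planimetric closure at that first, later confirmed, 0 cm² image. Date Equation 4a at the first investigator-noted closure that is later confirmed.
- Follow-up visits depend on the investigator calling closure, so a wound at 0 cm² still called open at Week 12 leaves the study with no follow-up images (Protocol 7.1). Classify it as not confirmed.
- Treat missed follow-up images as SAP 9.1 does for the primary endpoint, as undetermined.
- Censor unclosed wounds at their last image. Equations 4a and 4b now give them no time at all.

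The cost is small: wording and reprogramming on images already scheduled. The rule for unconfirmed zeros leaves the planimetric endpoint partly dependent on the investigator's call, which the report should say. Because SAP section 12 shows that the photograph data had already been evaluated, the SAP should also record whether this definition was fixed before the planimetry data were analysed. If it was not, the definition should be labelled post hoc.
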